## 6.6 Medical History

Medical history will be coded using the Medical Dictionary for Regulatory Activities (MedDRA) Version 18.1 or greater and summarized by system organ class (SOC) and preferred term for each treatment group, and overall. At each level of summarization, a patient is counted once if he/she reported one or more medical history terms at that level.

## 6.7 Concomitant Medications/Therapies/Procedures

Concomitant medications/therapies/procedures are those that are taken/performed at any time after the first dose of study medication.

If the start day of a medication/therapy/procedure is missing, then if the month and year of the start date are on or after the date of randomization, the following rules will be applied:

- If month/year of the start date is equal or after the month/year of the date of randomization, the medication/therapy/procedure will be considered concomitant;
- If month/year of the start date is equal to the month/year of the date of randomization, and the end date is present, the end date will be used to determine if the medication/therapy/procedure stopped prior to randomization or after. If the end date is after, the medication/therapy/procedure will be considered concomitant; otherwise, if the medication/therapy/procedure stopped prior, then it will be considered to be prior;
- If month/year of the start date is equal to the month/year of the date of randomization, and the end date is a partial date, the medication/therapy/procedure will be considered concomitant;
- If, despite implementing the above conventions, the start date of the medication/therapy/procedure cannot be placed before, on, or after randomization, then the medication/therapy/procedure will be considered concomitant.

Concomitant medications will be coded using the The World Health Organization (WHO) Drug Dictionary (September 2015 or later) and summarized by drug class (ATC Level 3) and preferred term for each treatment group. MedDRA 18.1 will be used to map each reported therapy/procedure to a specific ATC Level 4 and PT.

The summaries will present the number and percentage of patients using each medication and each therapy/procedure, by treatment group and overall. Patients may have more than one medication (or

therapy/procedure) per drug class or preferred term. At each level of summarization, a patient is counted once if he/she reported one or more medications (or therapy/procedure) at that level.

## 6.8 Efficacy Analyses

### 6.8.1 Primary Endpoint Analysis

The primary efficacy analysis will estimate the proportion of responders, based on the primary endpoint, at the end of the DPC period, within the octreotide capsules and placebo arms. An assessment of superiority will be made using an exact logistic regression model, with covariates for treatment, baseline SRL dose (low vs mid or high) and baseline IGF-1 level ( $<$  median vs  $\geq$  median). If the two-sided p-value is  $< 0.05$ , octreotide capsules will be declared superior to placebo. The adjusted proportions, difference in proportions and associated two-sided 95% confidence intervals will be reported. In addition, the odds ratio and two-sided 95% confidence interval (CI) will be reported. The FAS will be the primary population used for this analysis, with the PP population used as a supportive analysis.

Patients who discontinue study medication during the DPC period for any reason will be classified as non-responders for the primary analysis, regardless of their IGF-1 values. [REDACTED]

To assess the impact of missing data on the primary endpoint, several sensitivity analyses will be conducted using multiple imputation.

[REDACTED]

The primary endpoint analysis results will be reported overall and by sub-groups (region, age, gender and race). The same statistical methodology applied to the primary endpoint analysis will be used for analyzing the primary endpoint by each sub-group.

Randomization, in theory, should provide balance of all baseline characteristics, between the two treatment groups. At the conclusion of the study, if there is an imbalance in any baseline characteristics felt to be clinically meaningful, the effect of this imbalance on the primary endpoint will be evaluated through inclusion of covariates for these characteristics into the primary model above. These analyses will be considered sensitivity analyses to investigate the robustness of the primary analysis.

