#### **8.4.3 Primary Efficacy Analysis**

The primary efficacy analysis will estimate the proportion of responders, based on the primary endpoint, at the end of the DPC period, within the octreotide capsules and placebo arms. An assessment of superiority will be made using an exact logistic regression model, with covariates for treatment, baseline SRL dose (low vs mid or high) and baseline IGF-1 level ( $<$  median vs  $\geq$  median). If the two-sided p-value is  $< 0.05$ , octreotide capsules will be declared superior to placebo. The odds ratio and two-sided 95% confidence interval (CI) will be reported. The FAS will be the primary population used for this analysis, with the PP population used as a supportive analysis.

To assess the impact of missing data on the primary endpoint, sensitivity analyses will be conducted using multiple imputation. Further details will be provided in the SAP.

The primary endpoint analysis results will also be reported by sub-groups (region, age, gender and race). The same statistical methodology applied to the primary endpoint analysis will be used for analyzing the primary endpoint by each sub-group.

Randomization, in theory, should provide balance of all baseline characteristics, between the two treatment groups. At the conclusion of the study, if there is an imbalance in any baseline characteristics felt to be clinically meaningful, the effect of this imbalance on the primary endpoint will be evaluated through inclusion of covariates for these characteristics into the primary model above. These analyses will be considered sensitivity analyses to investigate the robustness of the primary analysis.

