### 3.2 Sample Size

Approximately 50 patients will be enrolled into the DPC period of the study on either octreotide capsules or matching placebo, in a 1:1 ratio.

[Redacted]	[Redacted]	[Redacted]
[Redacted]	[Redacted]	[Redacted]
[Redacted]	[Redacted]	[Redacted]
[Redacted]	[Redacted]	[Redacted]
[Redacted]	[Redacted]	[Redacted]
[Redacted]	[Redacted]	[Redacted]
[Redacted]	[Redacted]	[Redacted]
[Redacted]	[Redacted]	[Redacted]

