#### **6.3.4 Sub Groups**

The following sub-groups will be investigated;

- Region (US sites vs. non-US sites)
- Gender
- Age
- Race

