## 6.5 Demographics and Baseline Summaries

Demographic and baseline characteristics will be summarized by treatment group for the FAS set and the OLE set, by treatment group and overall, using descriptive statistics. If the FAS and safety set are different, then summaries will also be presented for the safety set. No statistical hypothesis tests will be performed.

The following continuous demographics data will be summarized:

- Age at screening in years. Age will be derived from the year of birth (year of Study Day 0 – year of birth).
- Weight at screening in kg
- Height at screening in cm
- BMI at screening in kg/m^2. BMI is calculated as weight / height in meters squared.

The following categorical demographics data will be summarized:

- Age: <65 years old, ≥65 years old;
- Gender: Male, Female
- Ethnicity: Hispanic or Latino, Not Hispanic or Latino, Not Reported, Unknown
- Race: Asian, American Indian or Alaskan Native, Black African or African/American, Native Hawaiian or Pacific Islander, White/Caucasian, Other. If more than one race can be selected the patient will be presented in each racial category in the summary table(s).

The following continuous baseline disease characteristics data will be summarized:

- Time from Last Surgery (if applicable)
- Time from Last Radiation (if applicable)
- Average IGF-1 levels (in ULN values) at Baseline (Based on the Average of the 2 assessments within 2 weeks prior to randomization)
- GH levels in mg/mL at Baseline

The following continuous baseline disease characteristics data will also be included for the OLE only:

- Average IGF-1 levels (in ULN values) at Baseline of the OLE (Based on the Average of the last 2 assessments during the DPC period)
- GH levels in mg/mL at Baseline of the OLE (Based on the last value collected during the DPC period)

The following categorical baseline disease characteristics data will be summarized:

- Duration of Acromegaly: <10 years, 10-<20 years, ≥20 years, unknown. Duration will be calculated as the difference in years from the date of diagnosis to date of informed consent.
- Pituitary Tumor Characteristics: Microadenoma, Macroadenoma, Other

- Previous Treatments for Acromegaly any Time in the Past:  
Surgery only (Yes/No)
- Residual Tumor Size: No remnants, < 5mm, 5-10 mm, >10 mm
- Prior Injectable Treatment Octreotide LAR (low, middle and high doses) and Lanreotide (low, middle and high doses)

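### With about 50 patients, repeating the primary exact test inside each subgroup gives p-values that mislead or carry almost no information; counts and differences with intervals, without p-values, would serve better

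*SAP*

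**What the plan says.** SAP 6.8.1 sets the primary analysis: "An assessment of superiority will be made using an exact logistic regression model", with terms for treatment, prior SRL dose (low against middle or high) and baseline IGF-1 (below the median or not). The decision rule is "If the two-sided p-value is" below 0.05, "octreotide capsules will be declared superior to placebo". For subgroups the same section adds: "The same statistical methodology applied to the primary endpoint analysis will be used for analyzing the primary endpoint by each sub-group". Protocol 8.4.3 carries the same instruction, introduced by "The primary endpoint analysis results will also be reported by sub-groups (region, age, gender and race").

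The size of the trial is set in SAP 3.2: "Approximately 50 patients will be enrolled into the DPC period of the study on either octreotide capsules or matching placebo, in a 1:1 ratio".

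SAP 6.3.4 lists the four factors. Only region comes with levels, "Region (US sites vs. non-US sites"); age and race have none there. The only visible levels for those two are in the demographic summaries of SAP 6.5, which cut age at 65 and name six race categories, with a conditional rule: "If more than one race can be selected the patient will be presented in each racial category". SAP 3.1 stratifies randomization by prior SRL dose alone, so arm sizes are not balanced by design within any of the four factors.

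The multiplicity section, SAP 6.3.5, does not mention subgroups. No visible text gives a treatment-by-subgroup test, a minimum size, a pooling rule or a caution about reading subgroup p-values.

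**The concern.** A p-value inside one subgroup addresses whether treatment works in that subgroup. It does not address whether the effect differs between subgroups. When each part holds a fraction of 50 patients, a uniform effect will often cross 0.05 in one part and miss it in the other. A table of within-subgroup p-values invites the reader to take that as a difference.

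The second problem is sparseness. An exact test conditions on the margins. With few patients, and two further covariates conditioned on, few tables remain possible. The p-value then approaches 1 and the odds-ratio limits can become infinite. Such output describes the size of the subgroup more than the drug.

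What is at stake is how the results are read. A benefit that is the same for everyone could be reported as present in one region and absent in the other.

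**Working it through.** **Inputs**
- Total 50, taken as 25 per arm (SAP 3.2); two-sided 0.05 (SAP 6.8.1).
- Active response: the earlier open-label Phase 3 study in Protocol 1.3.2.2 kept 65% (98/151) at 7 months and 62% (93/151) at 13 months. I use 65%, with 60% and 50% as lower cases.
- Placebo response: not visible. Assumed 10%, 20% or 30%.
- Subgroup sizes: not given. Assumed 25/25 or 10/40.
- Race and age levels: assumed to follow SAP 6.5.

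**The plan's own figure.** The rates and power behind the sample size are redacted, so it cannot be reproduced. As a plausibility check, 65% against 20% with 25 per arm gives 88.5% power by Fisher's test, so about 50 patients is a reasonable size.

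**Discordance when the true effect is identical.** Let p1 and p2 be the power in two complementary subgroups. They contain different patients, so

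P(exactly one significant) = p1(1 − p2) + p2(1 − p1).

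Powers are exact enumerations with Fisher's test. Even halves are 12 v 13 and 13 v 12; the 10/40 split is 5 v 5 and 20 v 20.

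| Active / placebo | Overall power | Even halves | Exactly one | 10/40 split | Exactly one |
|---|---|---|---|---|---|
| 65% / 10% | 98.5% | 85.0%, 82.0% | 28% | 29.1%, 95.3% | 69% |
| 65% / 20% | 88.5% | 63.7%, 61.2% | 47% | 18.8%, 75.7% | 66% |
| 60% / 20% | 78.8% | 53.1%, 49.7% | 50% | 14.2%, 65.0% | 61% |
| 65% / 30% | 65.3% | 40.9%, 40.0% | 48% | 11.4%, 46.8% | 47% |
| 50% / 20% | 51.0% | 32.4%, 28.3% | 42% | 7.4%, 40.9% | 42% |

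Worked line for 60% / 20%: 0.531 × 0.503 + 0.497 × 0.469 = 0.267 + 0.233 = 0.50.

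For equal powers the formula is 2p(1 − p), which peaks at 50% when p = 50%. The 60% / 20% row sits at that peak.

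**The SAP's own test.** The exact conditional logistic test was simulated with 1,000 to 1,500 trials per scenario. The low-dose share was 10%, 25% or 50%, half the patients were above the IGF-1 median, and the covariates had no effect on response. Conditioning costs power: at 65% / 20% each even half has about 53–55%, against 61–64% by Fisher. Discordance was 34–52% for even halves and 41–89% for 10/40.

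**Smallest attainable p before covariates.** With n patients of whom k are on active drug, the most extreme table has probability 1/C(n, k). When the arms are equal, its mirror image doubles this. Taking the most favourable allocation:
- n = 5 (2 v 3): 1/10 = 0.100
- n = 6 (2 v 4): 1/15 = 0.067; for 3 v 3 it is 2/20 = 0.10
- n = 7 (3 v 4): 1/35 = 0.029
- n = 8 (3 v 5): 1/56 = 0.018; for 4 v 4 it is 2/70 = 0.029

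So p < 0.05 is impossible at six or fewer. At seven or eight it is possible but unlikely: 4 v 4 has power 5.3% at 60% / 20% and 7.3% at 65% / 20%.

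**After conditioning on both covariates (simulated).** The share of data sets in which p < 0.05 cannot be reached is 100% at n = 5–6, 98.5–99% at n = 8, about 80% at n = 10 and 21–23% at n = 15. Power is at most 0.3% at n = 8 and 3–8% at n = 10.

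**What an interaction test would do.** An exact (Zelen) homogeneity test at 0.05 called identical effects different in 0.4–2.0% of simulated trials. Its power with even halves is 21% when 65% / 20% holds in one half and there is no effect in the other. It is 6% when the second half is 40% / 20%.

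**The case against.** The strongest reply is that no decision rests on a subgroup. SAP 6.3.5 has one primary test and a fixed order for the secondary endpoints, and the superiority declaration belongs to the full analysis set. Protocol 8.4.1 says only that the endpoint is summarized by these factors, and it acknowledges the small numbers. This stands. A reader might infer that the subgroup tests threaten the primary result or its error rate; the documents do not support that.

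Second, the primary method already reports adjusted proportions, a difference and an odds ratio with intervals, so each subgroup would have effect estimates in any case. That is true, but those estimates come from the same conditioned model that degenerates in small groups, and the p-values remain beside them.

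Third, the six race categories, the counting of a patient in several of them and the cut at 65 come from the demographics section, and the multiple-race rule is conditional. A reader might take them as the defined efficacy subgroups. SAP 6.3.4 does not say so, and they are used here as an assumption.

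Fourth, a reader might suppose the plan sets out to show US against non-US consistency. It lists region as a subgroup to be investigated and states no such question or hypothesis.

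Finally, a block of SAP 6.8.1 just before the subgroup paragraph is redacted, so an interaction test there cannot be ruled out. The subgroup paragraph itself, SAP 6.3.4 and Protocol 8.4.3 show no redaction and contain none.

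**Conclusion.** The point holds as a matter of interpretation. As written, the plan produces within-subgroup p-values that will often disagree when effects are identical: about 28–50% of the time for even halves and 42–69% for a 10/40 split, by Fisher's test under the assumed rates. No single figure should be quoted. A reader might take 50% as typical, but it is the top of the range for even halves.

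Nor do the documents support saying that small race groups in general cannot reach p < 0.05. That is strictly so only for six or fewer patients. With both covariates conditioned on, it is nearly always so at eight, about 80% of the time at ten and about a fifth of the time at fifteen. The race distribution is not given, so how many groups fall in that range is unknown.

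A reader might also conclude that an interaction test would settle consistency. With about 21% power even when one half has no effect at all, it guards against false differences but cannot show that effects are alike. One term also does not fit a race factor with several, possibly overlapping, levels.

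The primary conclusion is unaffected. The change is worth making because it is cheap; the trial does not depend on it.

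**What to change.** Replace the subgroup-method sentence in SAP 6.8.1 and in Protocol 8.4.3 with:

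> For each subgroup level, n/N by arm and the unadjusted difference in proportions with an exact 95% CI will be shown, without within-subgroup p-values or covariate adjustment. Race will be collapsed to non-overlapping groups, and levels below a size fixed before unblinding (e.g. fewer than 5 per arm) will be pooled or given as counts only. For two-level factors, an exploratory treatment-by-subgroup interaction (homogeneity) test may be reported, with the statement that its power is low (about 21% even if the effect, assumed 65% vs 20%, is present in only one of two equal halves) and that non-significance does not show consistency.

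SAP 6.3.4 should also state the age cut and the race grouping used for efficacy. The threshold of 5 per arm is an example, not a derived value; what matters is that it is fixed before unblinding.

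The cost is wording in two documents and a simpler table. The sponsor gives up within-subgroup p-values and gets, at most, an interaction test with little power.

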## 6.8.2 Secondary Endpoint Analyses

Analyses will be presented using both the FAS and the PP analysis set.

For the analysis of the proportion of responders based on mean GH, only patients with a screening mean GH value of  $< 2.5$  ng/mL will be included in the analysis. GH response will be defined using the mean integrated GH value, based on 5 assessments, 30 minutes apart. Patients who discontinue treatment during the DPC period for any reason will be classified as non-responders for the GH response analysis, regardless of their GH values. If a patient is missing their week 36 mean integrated GH value, this value will be imputed using the the Markov Chain Monte Carlo (MCMC) method for multiple imputation as outlined above. The adjusted proportions will be obtained from an exact logistic regression model, with covariates for treatment, baseline SRL dose (low vs mid or high) and baseline GH level ( $<$  median vs  $\geq$  median). The adjusted proportions, difference in proportions and associated two-sided 95% confidence intervals will be reported. In addition, the odds ratio and two-sided 95% confidence interval (CI) will be reported.

The time to loss of response will be summarized using the Kaplan-Meier method, and treatment groups will be compared using a Log-Rank test. Time zero is defined as the date time of the first dose of study medication. For each time to loss of response endpoint, three different analyses will be reported, with each of the three different analyses using a different approach (as defined earlier) to account for patients who discontinue from the study prior to meeting the definition of loss of response.

A Fisher's Exact Test will be used to compare the proportion of patients who begin rescue treatment prior to and including week 36. The denominator for each group will be all patients randomized to that group. The numerator will be those who start rescue treatment prior to and including week 36. The proportions within each treatment group, difference in proportions and exact two-sided 95% confidence interval will be reported.

After the study has completed, if there is an imbalance in any baseline characteristics felt to be clinically meaningful, the effect of this imbalance on the secondary endpoints will be evaluated through inclusion of covariates for these characteristics into the models described above. These analyses will be considered sensitivity analyses to investigate the robustness of the primary analyses for the secondary endpoints.

[REDACTED]

[REDACTED]

[REDACTED]

[REDACTED]

[REDACTED]

[REDACTED]

[REDACTED]

[REDACTED]

[REDACTED]

[REDACTED]

[REDACTED]	[REDACTED]
[REDACTED]	[REDACTED]
[REDACTED]	[REDACTED] [REDACTED]

3.	
[Redacted text]
	
[Redacted text]

	
[Redacted text]
	
[Redacted text]

5.	
[Redacted text]
	
[Redacted text]

[REDACTED]	[REDACTED]
[REDACTED]	[REDACTED]
[REDACTED]	[REDACTED]

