### 3.1 Randomization

Eligible subjects will be randomized 1:1 to octreotide capsules or placebo using permuted block randomization. Randomization will be stratified by prior SRL dose (Low vs Middle or High)

SRL Injection Dose	Dose Level Category
Octreotide dose of 10 mg q4w Lanreotide dose of 60 mg q4w or 120 mg q8w	Low
Octreotide dose of 20 mg q4w Lanreotide dose of 90 mg q4w or 120 mg q6w	Middle
Octreotide dose of 30 mg q4w Lanreotide dose of 120 mg q4w	High

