### 5.1.2 Secondary Efficacy Endpoints

1. Proportion of patients who maintain GH response (i.e., GH < 2.5 ng/mL) at week 36, out of those who were responders (i.e., GH < 2.5 ng/mL) on SRL injections at Screening. GH response will be defined using the mean integrated GH value, based on 5 assessments, 30 minutes apart. Patients who discontinue treatment during the DPC period for any reason will be classified as non-responders for the GH response analysis, regardless of their GH values.
2. Time to loss of response: Loss of response is defined as the earliest time when the IGF-1 of 2 consecutive visits is  $> 1 \times \text{ULN}$ , after the patient is treated for at least 2 weeks with 4 capsules per day. The date time of the earliest of the 2 consecutive measurements will be used. To account for patients who prematurely discontinue treatment prior to meeting these criteria, three different approaches will be used (i.e., this endpoint will be defined in three different ways). The three different definitions that will be used are as follows; (A) they will be counted as having had an event (i.e., met the criteria) at the time of treatment discontinuation; (B) they will be censored at the time of their last available assessment, when the patient was known to have not lost response. If there is no post-baseline assessment for response status, the patient will be censored with a time to loss of response of 0; and (C) they will not be censored, but evaluated for response based on the data collected after discontinuation (i.e., as long as the patient is known to be a responder regardless of adherence to treatment. For all three approaches patients who complete the study without meeting these criteria will be censored at their last study visit during the DPC period (i.e., week 36). Although 3 different approaches will be used, only the first approach will be used with respect to determining success. The other 2 approaches will not be considered in the multiplicity adjustment and are considered exploratory.

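### Randomization is stratified by prior SRL dose, but the confirmatory log-rank tests for time to loss of response do not use the stratum (minor efficiency and consistency point)

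*SAP*

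**What the plan says.** SAP 3.1 describes 1:1 permuted-block allocation: "Randomization will be stratified by prior SRL dose (Low vs Middle or High"). The first two tests in the confirmatory sequence use that factor. The primary exact logistic model is fitted "with covariates for treatment, baseline SRL dose (low vs mid or high) and baseline IGF-1 level" (SAP 6.8.1), and the GH model "with covariates for treatment, baseline SRL dose (low vs mid or high) and baseline GH level" (SAP 6.8.2).

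For the two time-to-loss-of-response endpoints, the same section states: "The time to loss of response will be summarized using the Kaplan-Meier method, and treatment groups will be compared using a Log-Rank test". Protocol 8.4.4 and the synopsis use the same wording. That sentence has no redaction in it, so blacked-out text does not explain the missing stratum.

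These endpoints are second and third in the fixed order at two-sided 5% (SAP 5.1.2 and 6.3.5). An event can be reached only "after the patient is treated for at least 2 weeks with 4 capsules per day". Under approach A, the only one that decides success, patients who stop treatment early are handled so that "they will be counted as having had an event (i.e., met the criteria) at the time of treatment discontinuation".

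**The concern.** Stratified randomization holds the arms nearly balanced on prior SRL dose. If dose predicts loss of response, the log-rank numerator then varies less between trials than the unstratified variance formula assumes. The test rejects too rarely under the null and loses power under the alternative.

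The covariate clause at the end of SAP 6.8.2 does not fill the gap. It applies only "if there is an imbalance in any baseline characteristics felt to be clinically meaningful", which stratification makes unlikely for this factor. It yields a sensitivity analysis, not the confirmatory test. It works by "inclusion of covariates for these characteristics into the models described above", and a log-rank test has no covariates to add to.

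At stake are two confirmatory claims in a trial of about 50 patients, and only after the primary and GH endpoints have both succeeded.

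**Working it through.** **No plan figure to reproduce.** The readable text gives no power or hazard ratio for these endpoints, and the sample-size assumptions are redacted. From the documents come about 50 patients, 1:1 allocation, two strata, visits at Weeks 4 to 32 every four weeks plus 34 and 36, and the event definitions. All other inputs are assumptions.

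**Tests compared.** At each event time j, with d events among n at risk, of whom n1 are on octreotide and have d1 events:

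- U = Σ(d1 − d·n1/n)
- V = Σ d·(n1/n)(1 − n1/n)(n − d)/(n − 1)
- Unstratified: reject if U²/V > 3.841.
- Stratified: compute U and V within each stratum; reject if (ΣU)²/ΣV > 3.841.

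**Model 1, marginal power.** N = 50; low-dose stratum of 5, 15 or 25; blocks of 4 within stratum; exponential hazards; 50, 75 or 90% placebo events by Week 36; 0 or 15% discontinuation counted as events. There were 10,000 replicates per power cell (standard error of the paired difference 0.15 to 0.36 points in spot checks) and 20,000 per null cell. Stratified minus unstratified power, in points:

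| Treatment HR | Stratum HR 1 | 1.5 | 2 | 3 |
|---|---|---|---|---|
| 0.25 | −0.9 to −0.1 | −0.2 to +0.6 | +0.2 to +1.8 | +0.4 to +5.4 |
| 0.4 | −1.0 to −0.2 | −0.5 to +1.1 | +0.2 to +3.8 | +1.4 to +10.3 |
| 0.55 | −1.1 to +0.2 | −0.1 to +1.3 | +0.2 to +4.3 | +1.4 to +11.4 |

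Worked cell (treatment HR 0.4, 75% placebo events, 15% discontinuation, 30% low dose):

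- Stratum HR 1: 0.578 − 0.585 = −0.007
- Stratum HR 2: 0.619 − 0.592 = +0.027
- Stratum HR 3: 0.635 − 0.556 = +0.079

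Type I error, unstratified: 4.9–5.8% (stratum HR 1), 4.1–5.3% (HR 2), 3.1–4.9% (HR 3). Stratified: 4.9–5.7% throughout.

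**Separate simulation.** 4,000 trials per cell, 30% of placebo patients event-free at Week 36, treatment HR 0.4 for power and 1 for type I error. The standard error is about 0.75 points for power and 0.35 for type I error.

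| Low-dose share | Stratum HR | Power, unstratified / stratified | Difference (points) | Type I error, unstratified / stratified |
|---|---|---|---|---|
| 20% | 1 | 0.640 / 0.635 | −0.5 | 5.0% / 5.0% |
| 20% | 2 | 0.642 / 0.658 | +1.6 | 4.6% / 5.4% |
| 20% | 4 | 0.610 / 0.662 | +5.2 | 3.5% / 5.6% |
| 35% | 1 | 0.658 / 0.654 | −0.4 | 4.9% / 5.3% |
| 35% | 2 | 0.629 / 0.649 | +2.0 | 4.4% / 5.3% |
| 35% | 4 | 0.564 / 0.658 | +9.4 | 2.6% / 5.6% |
| 50% | 1 | 0.645 / 0.640 | −0.5 | 5.6% / 6.0% |
| 50% | 2 | 0.620 / 0.649 | +2.9 | 3.8% / 4.8% |
| 50% | 4 | 0.530 / 0.669 | +13.9 | 2.4% / 5.9% |

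Both tests can run slightly above 5% at this sample size. The unstratified test drops well below 5% only when dose is strongly prognostic.

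**Model 2, with the testing order.** IGF-1 was simulated visit by visit, with dose step-up on the two IGF-1 escalation rules, the four-capsule and two-visit conditions of endpoint 2, and approach A. The primary test was approximated by a continuity-corrected Cochran–Mantel–Haenszel test.

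| Stratum HR (about) | Change in endpoint 2 power, marginal (points) | Change in chance that primary and endpoint 2 both succeed (points) |
|---|---|---|
| 1 | −0.3 to +0.2 | −0.2 to 0.0 |
| 1.4 | +0.1 to +2.3 | −0.1 to +0.2 |
| 2 | +0.2 to +10.0 | at most +0.7 |
| 3 | +0.5 to +28 | +0.1 to +2.7 |

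One cell shows why the second column is small (treatment HR 0.39, stratum HR 2.0, 30% low dose, 15% discontinuation). Endpoint 2 power rises from 0.808 to 0.863. The primary succeeds in 0.424 of trials, and both succeed in 0.414 unstratified against 0.417 stratified. Once the primary has succeeded, the unstratified test already succeeds in 0.414/0.424 = 97.6% of trials, against 0.417/0.424 = 98.3% stratified.

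**The case against.** The strongest reply is that this is a preference. The unstratified log-rank test is valid and fully specified, it matches the unstratified Kaplan–Meier summary, and nothing in the SAP promises that every secondary test will use the stratum. The gain that matters, after the primary succeeds, is close to zero unless dose is strongly prognostic, and the readable text gives no evidence that it is. Consistency is also only partial. The primary and GH models adjust for a median split of baseline IGF-1 or GH as well, and endpoint 4 uses an unstratified Fisher's exact test. A sparse-stratum rule adds a data-dependent step.

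Most of this stands as a limit on importance. The inputs are assumed. Model 2 is not calibrated to the redacted power table: its example has primary power of only 0.424, so its gated figures are indicative. It models neither symptom-driven titration nor the GH test, which must also succeed. Stratifying endpoints 2 and 3 would leave endpoint 4 as it is.

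It does not remove the point. The plan treats SRL dose as worth using in the design and in the first two confirmatory tests, then drops it from the next two without a reason. Under Model 1, the marginal trade is about one point lost at worst if dose is not prognostic against several gained if it is.

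**Conclusion.** The point holds as a minor, optional improvement. There is no error in validity, type I error control, sample size or the primary analysis. Leaving out the stratum costs essentially nothing if prior SRL dose is not prognostic. It costs a few points of marginal power at a stratum hazard ratio of 2, and up to roughly 10 or more at 3 to 4. The effect on confirmatory success is much smaller, below one point at a stratum hazard ratio of 2. The direction is well supported, since the separate simulation agrees with Model 1. The size depends on the assumed prognostic strength, low-dose share, event rate and treatment effect, none of which the readable text gives.

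**What to change.** Before unblinding, amend SAP 6.8.2:

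- For endpoints 2 and 3 under approach A, name a log-rank test stratified by the randomization stratum (Low vs Middle or High) as the confirmatory test.
- State a rule, applied to blinded pooled counts, for reverting to the unstratified test if a stratum is too sparse. Fewer than 5 events in either stratum is one example.
- Keep the unstratified log-rank test as a sensitivity analysis.

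If the sponsor prefers the unstratified test, one sentence giving the reason is enough. The same sentence could cover the Fisher test for endpoint 4.

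The cost is one or two sentences. SAP section 1 says the SAP prevails over the protocol and asks for an amendment when the primary endpoints or analyses change; on its natural reading, this secondary change falls outside that. Aligning protocol 8.4.4 and the synopsis is optional.

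The statistical cost if dose is not prognostic is about 1 point of marginal power at most in Model 1, and about 0.2 points once the primary must also succeed in Model 2. With the 5-event rule, simulated type I error is 4.3–5.7%. The rule reverts in 59–100% of trials if 10% of patients are low dose (the change then does almost nothing, −0.4 to +0.1 points), in 0–81% at 30%, and in 0–36% at 50%.
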